7.0 Compensation and Costs

Focus Groups: For their participation in the focus groups, hypertension patient participants will receive a \$50 Amazon gift card. Healthcare providers will receive \$75 Amazon gift card.

Patient 6-week pre-post evaluation. Participants will receive \$20 in an Amazon gift card for completion of baseline assessments (e.g. blood pressure (BP) measures). At the completion of the pre-post study, patient participants will be offered \$130 Amazon gift card for their time. In total, pre-post participants will receive \$150 in Amazon gift card.

There will be no costs to participants.

8.0 Study Withdrawal/Discontinuation

Any participant may choose to withdraw from the focus group study or the pre-post study at any time and for any reason. Participants will need simply to contact the investigator.

9.0. Outcome Measures

HTN med adherence will be assessed by the Adherence to Refills and Medication Scale (ARMS), a well-validated self-report measure used widely in studies with minority patients and/or those with low literacy (Buis et al., 2019; Kripalani et al., 2009; McNaughton et al., 2014). We will also use Segeral et al. (2010) 3-item adherence measure, as in our prior research (Pagan-Ortiz et al., 2019). Validated self-report measures correlate with clinical outcomes and are desirable to use in research with African American patients, who may resist providing bio-specimens due to historical mistrust (Ewing et al., 2019, Stirratt et al., 2015). Lastly, electronic pill bottles are cumbersome, expensive, and often ineffective for promoting and tracking adherence (Choudhry et al., 2017; Volpp et al., 2017).

Secondary: Adherence self-efficacy will be assessed with the HTN med adherence self-efficacy scale (MASES) (Ogedegbe et al. 2003). HTN knowledge will be assessed using the NHLBI HTN Knowledge Scale (Carter-Edwards et al., 2002). Stress burden will be assessed using Perceived Stress Scale (Cohen et al., 1983). **Exploratory:** BP will be measured at baseline and 6 weeks. **Primary Hypothesis:** Participants will show greater HTN med adherence at 6 wks compared to baseline.

Secondary Hypothesis: Participants will show greater HTN adherence self-efficacy, greater HTN knowledge, and lower stress burden at 6 wks compared to baseline. **Exploratory Hypothesis:** Participants will show a decrease in systolic BP at 6 wks compared to baseline. **Data analyses:** We will conduct one-tailed paired t-tests at the .05 level for primary and exploratory hypotheses and McNemar's chi square for secondary hypotheses. Data from our Phase 1 evaluation of short-term effectiveness will be used to determine the sample size necessary for an adequately-powered Phase 2 RCT.

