10.0 Statistical Considerations

Because this is a feasibility study, the pre-post evaluation sample size is not based on power calculations. In Phase 2, a sample size will be created with a power of at least 90% with a two-sided alpha level of .05.

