### **Analysis plan:**

**Measures: Primary:** HTN med adherence will be assessed by the Adherence to Refills and Medication Scale (ARMS), a well-validated self-report measure used widely in studies with minority patients and/or those with low literacy (Buis et al., 2019; Kripalani et al., 2009; McNaughton et al., 2014). We will also use Segeral et al. (2010) 3-item adherence measure, as in our prior research (Pagan-Ortiz et al., 2019). (NB: The team revised the adherence measure approach to use a single measure, namely the Wilson et al. (2016) Self-Report Medication Adherence scale.) **Secondary:** Adherence self-efficacy will be assessed with the HTN med adherence self-efficacy scale (MASES) new (Ogedegbe et al. 2003). Stress burden will be assessed using Perceived Stress Scale (Cohen et al., 1983). HTN knowledge will be assessed using the NHLBI HTN Knowledge Scale (Carter-Edwards et al., 2002). **Primary Hypothesis:** Participants will show greater HTN med adherence at 6 wks compared to baseline. **Secondary Hypothesis:** Participants will show greater HTN adherence self-efficacy, greater HTN knowledge, and lower stress burden at 6 wks compared to baseline.

**Data analyses:** We will conduct one-tailed paired t-tests at the .05 level for primary hypotheses. Data from our Phase 1 evaluation of short-term effectiveness will be used to determine the sample size necessary for an adequately-powered Phase 2 RCT.

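### McNemar's chi-square is assigned to three secondary scale outcomes with no cut-point defined, and the SAP names no secondary test

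*Protocol*

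**What the plan says.** Protocol section 9.0 lists three secondary outcomes: adherence self-efficacy (MASES), hypertension knowledge ("HTN knowledge will be assessed using the NHLBI HTN Knowledge Scale") and stress burden (Perceived Stress Scale). The secondary hypothesis is "Participants will show greater HTN adherence self-efficacy, greater HTN knowledge, and lower stress burden at 6 wks compared to baseline".

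The same section sets the tests. For two of the three tiers: "We will conduct one-tailed paired t-tests at the .05 level for primary and exploratory hypotheses". For the remaining tier: "McNemar's chi square for secondary hypotheses".

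The SAP repeats the three measures and the secondary hypothesis. Its only sentence on tests is "We will conduct one-tailed paired t-tests at the .05 level for primary hypotheses".

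Protocol section 10.0 adds that "the pre-post evaluation sample size is not based on power calculations".

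**The concern.** McNemar's test uses only participants whose yes/no classification changes between two occasions. It tests whether a proportion has moved, whereas the secondary hypotheses are about levels of a score. Applying it requires each scale to be cut in two, and the plan does not say where.

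Three things follow:

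- **Open choice.** A cut-point chosen after the 6-week scores are seen can affect whether the result is significant.
- **Lost information.** Splitting a score discards all change that does not cross the cut, which lowers power.
- **Less useful output.** The result is a change in proportions, not the mean change and SD that would help in planning Phase 2.

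There is also a conflict between the documents. The protocol names a secondary test and the SAP names none, so a reader of both cannot tell which analysis applies.

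**Working it through.** **1. Text check**

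| Item | Protocol 9.0 | SAP |
|---|---|---|
| Secondary measures | Three scales | Same three scales |
| Form of hypothesis | Greater, greater, lower | Same |
| Secondary test | McNemar's chi-square | None named |
| Cut-point or binary coding | None | None |
| Sidedness and alpha for the secondary test | Not stated; one-tailed .05 is attached to the t-tests | Not stated |

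Neither document prints the scoring of the scales. That they give multi-level scores is inferred from their being called scales and from the greater/lower wording. The primary outcome, also a self-report adherence scale with a hypothesis of the same form, is given a paired t-test. The protocol offers no reason for treating the secondary scales differently. In the SAP the secondary hypothesis has its own label, so a sentence limited to primary hypotheses does not cover it.

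**2. Illustration of the cost**

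The plan has no figure to reproduce: it gives no n, SD, correlation, effect or cut-point. Every input below is assumed.

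Base case: n = 30 completers, pre-post correlation r = 0.6, standardised change dz = 0.5 (mean change ÷ SD of the differences).

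*Paired t-test (exact, noncentral t).* Noncentrality = dz × √n = 0.5 × √30 = 2.74, with n − 1 = 29 degrees of freedom. The critical values are 1.699 (one-sided .05) and 2.045 (two-sided .05). Power is 0.848 one-sided and 0.754 two-sided.

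*McNemar (40,000 simulated pilots).* Scores are bivariate normal with unit SD. The shift is dz × √(2(1 − r)) = 0.5 × √0.8 = 0.447 SD. Each score is cut at the baseline sample median. With u participants moving up and w moving down, z = (u − w)/√(u + w), without continuity correction. Power is 0.548 one-sided and 0.364 two-sided. With continuity correction it is 0.378 and 0.262.

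Varying one input at a time:

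| Scenario | t, one-sided | McNemar, one-sided | t, two-sided | McNemar, two-sided |
|---|---|---|---|---|
| Base case | 85% | 55% | 75% | 36% |
| n = 20 | 70% | 38% | 56% | 25% |
| n = 50 | 97% | 74% | 93% | 61% |
| dz = 0.3 | 48% | 27% | 36% | 15% |
| dz = 0.7 | 98% | 79% | 96% | 63% |
| r = 0.4 | 85% | 61% | 75% | 44% |
| r = 0.8 | 85% | 42% | 75% | 27% |
| Cut at 25th percentile | 85% | 43% | 75% | 29% |
| Cut at 75th percentile | 85% | 48% | 75% | 32% |

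The one-sided gap at base case is 85 − 55 = 30 points. Across the table it runs from 98 − 79 = 19 to 85 − 42 = 43 points. The Wilcoxon signed-rank test at base case has 83% one-sided and 73% two-sided, so the loss comes from dichotomising and not from avoiding the t-test.

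**3. Effect of a free cut-point**

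With no true change (n = 30, r = 0.6), each fixed cut at the 25th, 50th or 75th population percentile gives a one-sided false-positive rate of about 5%. Taking the best of the three gives 13.3% (13.4% at n = 20, 13.5% at n = 50). With cuts set at the sample percentiles it is about 12% at n = 20 and n = 30, and 13% at n = 50.

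**The case against.** The strongest reply is that the plan is incomplete and not wrong. McNemar is legitimate on pre-specified categories, or item by item on correct/incorrect knowledge answers, and the documents do not print the scoring. That is true, but no such coding is described. If one is intended, it has to be stated, so the gap remains on this reading too.

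Second, the SAP may have dropped McNemar deliberately. It records a revision of the adherence measure, and its analysis sentence omits both the exploratory and the secondary tests. The documents do not settle this. If McNemar was dropped, the secondary hypotheses have no test, the power comparison concerns an abandoned method, and the protocol still says otherwise. The two must be reconciled in either case.

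Third, the power figures rest wholly on assumed inputs, and the pilot has no power target to miss. Nothing suggests that anyone intends to search for a cut-point. This stands: the figures show direction and rough size and are not properties of this trial.

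Fourth, the harm to Phase 2 planning is modest. The protocol does not say the secondary scales will size Phase 2, and mean change and SD could be reported whichever test is used. This also stands.

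**Conclusion.** The concern holds. The protocol's secondary test does not fit the outcomes as described. It cannot be run without a dichotomisation that neither document states, and the SAP leaves the secondary hypotheses without a test. This conclusion rests on the text and on reading the three scales as multi-level scores; it does not depend on the simulations.

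The illustrated cost, on assumed inputs, is roughly 20 to 40 points of one-sided power, plus a false-positive rate of about 12–13% if the best of three cut-points were taken.

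This should be fixed, but its reach is limited. The outcomes are secondary, the study is a feasibility pilot not sized on power, and the t-tests for the primary and exploratory hypotheses are unaffected.

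**What to change.** In protocol section 9.0, replace the McNemar clause with text to this effect, and put the same text in the SAP's data analyses paragraph:

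> Each secondary hypothesis will be tested with a one-tailed paired t-test at the .05 level on the total scale score (direction: higher self-efficacy, higher knowledge, lower stress). A Wilcoxon signed-rank test will be the sensitivity analysis. Mean change, its SD and a two-sided 95% confidence interval will be reported for estimation.

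One-tailed .05 matches the protocol's other hypotheses. The two-sided interval matches the Phase 2 plan in protocol section 10.0: "In Phase 2, a sample size will be created with a power of at least 90% with a two-sided alpha level of .05". Because a one-sided p-value between .025 and .05 goes with a two-sided 95% interval that includes zero, add that the test governs the hypothesis and the interval is for estimation only.

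If a yes/no analysis is wanted, keep McNemar as supportive and state the cut-point for each scale, the alpha and the sidedness before the 6-week scores are examined.

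The cost is a few sentences in each document. The scales are already planned at baseline and 6 weeks, so no new data are needed.

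### Is it a flaw that the plan does not say which Phase 1 quantity will set the Phase 2 sample size?

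*Protocol*

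**What the plan says.** Protocol section 9.0 ends its analysis paragraph with the statement "Data from our Phase 1 evaluation of short-term effectiveness will be used to determine the sample size necessary for an adequately-powered Phase 2 RCT". The SAP's analysis plan makes the same commitment: "Data from our Phase 1 evaluation of short-term effectiveness will be used to determine the sample size". Neither document says whether a mean change, a standard deviation, a pre-post correlation or an attrition rate is meant.

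The primary hypothesis in section 9.0 is a within-person one: "Participants will show greater HTN med adherence at 6 wks compared to baseline". The Protocol tests it as follows: "We will conduct one-tailed paired t-tests at the .05 level for primary and exploratory hypotheses". The SAP agrees for the primary hypothesis: "We will conduct one-tailed paired t-tests at the .05 level for primary hypotheses". No concurrent control group is described.

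Protocol section 10.0 says of the pilot: "Because this is a feasibility study, the pre-post evaluation sample size is not based on power calculations". Of the later trial it says: "In Phase 2, a sample size will be created with a power of at least 90% with a two-sided alpha level of .05". The available text gives no pilot sample size, and for Phase 2 no target difference, SD or allocation ratio.

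**The concern.** A randomised trial is sized on a between-arm difference. A single-arm change over 6 weeks mixes any effect of the text-message system with everything else that moves over that time, such as regression to the mean, the attention that comes with being studied, and a repeated self-report questionnaire. If that change were used unaltered as the Phase 2 target, and only part of it were due to the intervention, Phase 2 would be too small for its promised 90% power. The sentence ties Phase 2 sizing to data on effectiveness, and the only effectiveness analysis defined for the primary outcome is the paired comparison, so this reading comes easily. The same data can also properly supply an SD, a correlation and an attrition rate, and the text does not choose between the uses.

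**Working it through.** **Inputs.** From Protocol section 10.0: Phase 2 power 90%, two-sided alpha 0.05. Everything else is assumed: the share k of the target that is real, the pilot size n, and the pre-post correlation rho. The documents contain no Phase 2 sample size to reproduce.

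The required standardised distance is z(0.975) + z(0.90) = 1.960 + 1.2816 = 3.2415.

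**Use A: the pilot change is the target, SD treated as known.** If the true between-arm difference is k times the target, power = P(Z > 1.960 − 3.2415k).

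- k = 0.90: P(Z > −0.957) = 0.831
- k = 0.75: P(Z > −0.471) = 0.681
- k = 0.50: P(Z > 0.339) = 0.367
- k = 1.10 (control-arm adherence falls): P(Z > −1.606) = 0.946

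Power equals 80% at k = (1.960 + 0.842)/3.2415 = 0.864.

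If Phase 2 is sized without baseline adjustment but analysed with it, 3.2415k is divided by sqrt(1 − rho²). For k = 0.90, 0.75 and 0.50 this gives 0.921, 0.802 and 0.465 at rho = 0.5, and 0.983, 0.926 and 0.622 at rho = 0.7. So even under this use a shortfall is possible but not certain.

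**Use B: only the SD comes from the pilot, target set elsewhere.** Phase 2 n is then proportional to the pilot variance s². Power = P(Z > 1.960 − 3.2415·k·s/σ), averaged over (n − 1)s²/σ² ~ chi-square on n − 1 degrees of freedom.

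With an exactly right target (k = 1), mean power is 0.864, 0.876 and 0.885 for n = 20, 30 and 50. Against 0.90 the loss is 1 to 4 points, compared with 7 to 53 points under use A (0.900 − 0.831 and 0.900 − 0.367). Set side by side, these look like a strong argument for B.

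**Like for like.** That contrast gives A a wrong target and B a right one. Nothing in the documents supports a target from elsewhere being exact. With the same overstatement in both:

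| True share k of target | A | B, n = 20 | B, n = 50 |
|---|---|---|---|
| 0.90 | 83% | 80% | 82% |
| 0.75 | 68% | 66% | 67% |
| 0.50 | 37% | 36% | 37% |

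B is no better than A. Its mean also hides a spread: at n = 20 and k = 1, the 10th percentile of s/σ is sqrt(11.65/19) = 0.783, so one pilot in ten gives power of about 72% or less. (A takes the SD as known; if its SD also came from the pilot, A would have the same values as B.) What costs power is a wrong target, whatever its source.

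**What the pilot delivers anyway.** The paired t-test needs each participant's baseline and week-6 score. From those scores come both SDs, the SD of the change and the correlation. Enrolled participants without a week-6 score give the attrition. None of this needs extra data, and section 11.0 provides for long-term storage of the pre-post data.

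**The case for a change.** The best case for the concern is that the commitment is written into the Phase 1 documents, that informing Phase 2 is a stated use of this pilot, and that one sentence could rule out the unsound reading. The quantity also matters in practice. Suppose the pilot showed a paired standardised change of 0.5. Converting it to the between-arm scale by d = 0.5·sqrt(2(1 − r)), with equal SDs, gives d = 0.592, 0.500 or 0.387 for r = 0.3, 0.5 or 0.7. That means 61, 85 or 141 per arm at 90% power and two-sided 0.05 with 1:1 allocation. Without the correlation, even the pilot's own result cannot be used properly.

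Some of this stands. The text does not name the quantity, and a one-arm change does not by itself identify a between-arm difference. But that change is not useless: it can be combined with an assumed or external control-arm change, so using effectiveness data is not in itself an error. The correlation can be computed from the planned data whether or not the plan announces it. A sentence naming SD, correlation and attrition would still leave the target difference, the one input that drives the loss, to the Phase 2 protocol. It would also leave open which SD and which adherence scale are meant, since the SAP notes a change to a single scale that Protocol section 9.0 does not list. That mismatch is a separate matter.

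**Conclusion.** The concern does not hold. The documents omit a detail about a later trial; they do not prescribe a wrong calculation. Section 10.0 fixes the power and two-sided alpha for Phase 2, and the remaining inputs belong in that trial's own protocol. No estimate, test or conclusion of the pilot changes whichever quantity is later used.

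The power losses of 7 to 53 points rest on assumed shares of 90% to 50%, no baseline adjustment, and a decision the documents do not make. Under the same assumed error in the target, taking only the SD from the pilot gives 80%, 66% and 36% at n = 20, so no advantage is shown for restricting how Phase 1 data are used. Naming the quantities would be a drafting preference. This conclusion rests on the text available, in which no passage takes the one-arm change as the Phase 2 target.

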10.0 Statistical Considerations

Because this is a feasibility study, the pre-post evaluation sample size is not based on power calculations. In Phase 2, a sample size will be created with a power of at least 90% with a two-sided alpha level of .05.

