2.0 Goals

We propose a digital adherence solution to help reduce HTN-related disparities among African Americans, called Memento.HTN, which is innovative in three key ways: 1) it is the first-ever linked digital provider platform and patient SMS text system for HTN medication adherence; 2) it is culturally-tailored for African Americans with HTN; and 3) it has unique monitoring functionality allowing providers to monitor individual patient adherence, support 'new start' patients, who are at increased risk for non-adherence, and to track group adherence rates by drug class, pill format, and patient demographics in order to inform clinical therapeutics. Requiring only minutes of staff or prescriber monitoring per day, the Memento system simplifies and facilitates provider delivery of adherence support. The provider platform sends patients interactive SMS pill reminders plus culturally-sensitive motivational, educational, spiritual/stress-supportive, and customizable texts, along with texts that target intentional non-adherence. Importantly, Memento allows 2-way communication between providers and patients, and automatically alerts providers when a patient is having clinically-significant pill lapses.

Specific Aim 1: Develop an individually-tailored, culturally-sensitive digital health intervention comprised of a provider platform and linked patient SMS system to promote medication adherence in African Americans with HTN.

Specific Aim 2: Implement a 6-wk pilot to evaluate feasibility and short-term effectiveness for improving adherence.

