During the 6-week study period, patient participants will receive several types of text messages: daily interactive pill reminders, educational, motivational, spiritual/stress-supportive. Individuals that are 'new starts,' i.e. have been prescribed HTN meds within the last 8 weeks, will receive additional texts to support their implementation and persistence with their HTN med regimen. Study staff will monitor backend data to

determine if any patient participants are not opening their text messages or if a patient has missed pills 2 out of 7 days, which Dr.[name] has advised us is a clinically-significant pill lapse. In such instances, study staff will reach out to patients to see if they need support to help them with engagement.

At 6 weeks, patient participants will receive a phone call and text informing them it is time to re-take baseline assessments as well as to participate in end-of-study focus group (or individual interview). At the end of the study, participants will be invited to participate in a zoom focus group with up to 10 other participants or an individual interview (zoom or phone) to provide feedback on the Memento system.

After re-taking baselines and participating in the end-of-study focus group/interview, pre-post participants will be emailed a link for \$130 Amazon gift card.

6.0 Reporting of Adverse Events or Unanticipated Problems involving Risk to Participants or Others

We consider the risks to participants in both the patient and the healthcare provider focus groups to be minimal, i.e. there is a minor risk that other members of the patient focus group will know that a given participant is taking HTN medications. We will be clear in consenting patients that such a risk exists. There is a small risk of the time demand of the focus group will feel burdensome. We will make clear in informed consents for patients and for providers that they may end their participation at any time if the time demand becomes a problem.

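### Must the six-week pre-post pilot state a planned number of participants or a precision target, given that it tests effectiveness and feeds the Phase 2 sample size?

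*Protocol*

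**What the plan says.** Protocol section 10.0 has two sentences. The first reads "Because this is a feasibility study, the pre-post evaluation sample size is not based on power calculations". The second concerns Phase 2 only: at least 90% power at a two-sided .05 level.

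No pilot enrolment figure, range, cap or dropout allowance appears in the sections on eligibility (3.0), recruitment (4.0), procedures (5.0) or withdrawal (8.0), or in the SAP's analysis plan. The only head-count tied to pilot participants is the size of a feedback session at the end of the study: "a zoom focus group with up to 10 other participants or an individual interview".

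The pilot has more than one purpose. Specific Aim 2 in section 2.0 is to "Implement a 6-wk pilot to evaluate feasibility and short-term effectiveness for improving adherence". Section 9.0 gives the primary hypothesis, "Participants will show greater HTN med adherence at 6 wks compared to baseline", and its test: "We will conduct one-tailed paired t-tests at the .05 level for primary and exploratory hypotheses". The SAP says the same of the primary hypothesis: "We will conduct one-tailed paired t-tests at the .05 level for primary hypotheses". Section 9.0 adds, and the SAP repeats, "Data from our Phase 1 evaluation of short-term effectiveness will be used to determine the sample size necessary for an adequately-powered Phase 2 RCT".

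**The concern.** Calling the study a feasibility study explains why there is no power calculation. It does not explain why there is no number at all. Two of the pilot's stated uses depend directly on n: the .05 test of the primary hypothesis, and the estimates handed on to Phase 2.

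Without a planned n, a reader cannot say in advance what change the test could detect, how wide the interval for that change would be, or how firm a base the Phase 2 calculation would have. Nor is there a written point at which recruitment ends. If the pilot proved very small, a trial meant to have 90% power could rest on a badly estimated SD.

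**Working it through.** **Inputs.** From the documents: one-tailed paired t-test at .05 (Protocol 9.0, SAP); Phase 2 at 90% power, two-sided .05 (Protocol 10.0). The documents give no n, effect size, SD or dropout rate for the pilot, so there is no figure of the plan's own to reproduce. The values of n (completers) and of the standardised change d below are assumptions, with normal data.

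**Step 1: what different n would give.**

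- Power: P(T > t(.95, n−1)), with T noncentral t on n−1 df and noncentrality d√n.
- 95% half-width for the mean change, in SDs of the change: t(.975, n−1)/√n. For n = 30 this is 2.045/5.477 = 0.373.
- 95% limits for the true variance as multiples of the estimate: (n−1)/χ²(.975, n−1) to (n−1)/χ²(.025, n−1). Required Phase 2 N is proportional to the variance, so the same factors apply to N.

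| n | d for 80% power | Power at d = 0.3 | Power at d = 0.5 | Half-width (SD) | Variance factor |
|---|---|---|---|---|---|
| 10 | 0.85 | 22% | 43% | 0.72 | 0.47–3.33 |
| 20 | 0.577 | 36% | 70% | 0.47 | 0.58–2.13 |
| 30 | 0.465 | 48% | 85% | 0.37 | 0.63–1.81 |
| 50 | 0.357 | 67% | 97% | 0.28 | 0.70–1.55 |
| 100 | 0.25 | 91% | 100% | 0.20 | 0.77–1.35 |

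An observed retention of 90% would have exact 95% limits of 68–99% (18/20), 73–98% (27/30) or 78–97% (45/50).

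**Step 2: what this could do to Phase 2.** Suppose only the SD is carried forward, and that it is also the SD of the outcome in a two-arm trial. True power falls below 80% when s²/σ² is below ((0.842 + 1.960)/(1.282 + 1.960))² = (2.802/3.242)² = 0.747. The chance of that is 22.8%, 16.6% and 9.5% for n = 20, 30 and 50. Simulation with the t-test, at a design difference of 0.5 SD, gives 22.0%, 15.8% and 8.7%.

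**Step 3: does writing n down change any of this?** Put N = 30 into section 10.0 and suppose 30 complete. The detectable d is still 0.465, the half-width still 0.37 SD, the variance factor still 0.63–1.81, and the Phase 2 risk still about 16%. All of these depend on the n achieved. None depends on whether it was announced.

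**Step 4: would a null result be uninterpretable?** No, because the interval is available at analysis. Two invented examples:

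- With n = 30 and a mean change of 0.25 SD, t = 0.25 × 5.477 = 1.37, below the one-tailed critical value of 1.70. The interval is 0.25 ± 0.37, or −0.12 to 0.62 SD, which is plainly inconclusive.
- With n = 100 and a mean change of 0.05 SD, t = 0.05 × 10 = 0.5, also non-significant. The interval is 0.05 ± 0.20, or −0.15 to 0.25 SD, which excludes an improvement above 0.25 SD.

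The achieved n and the interval separate the two cases without any planned n.

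**Step 5: when does Phase 2 need the number?** When Phase 2 is designed, after the pilot. The pilot's n, SD and retention will then be known, and the uncertainty in them can be calculated as above.

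**The case for a change.** The best case for a change is that the statistical section says what the sample size is not based on and never what it is. The remedy would be cheap: a few sentences giving the planned number, the expected completers and the reason, with no new procedures. A stated number would let others judge beforehand whether the pilot can serve its two quantitative uses, and would fix the end of recruitment in a plan that tests at a set .05 level.

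Part of this stands. The text available gives no number, and a stated one would be good reporting. Even a practical reason, such as budget or recruitment capacity, would do.

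The rest is weaker. An open recruitment end distorts a test if enrolment stops because of the results, and the documents describe no interim look at the adherence scales. The staff monitoring in section 5.0 concerns unopened texts and missed pills, and it serves to offer support. Requiring a precision rationale would replace the sponsor's actual reason with one it may not have used. A promise to allow for interval width when sizing Phase 2 names no method and alters no Phase 1 result. Finally, title, signature, contact and consent pages are missing from the copy reviewed, so the number may be stated there.

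**Conclusion.** No change to the plan follows. The gap is one of documentation: the available text gives no pilot sample size and no reason beyond the absence of a power calculation. The plan is open about that absence, claims no power or precision, and leaves the formal calculation to Phase 2, which is a fair choice for a pilot.

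The uncertainty at stake is considerable: a half-width of 0.28 to 0.47 SD and about a 9% to 22% chance of a Phase 2 trial with under 80% power, for 50 down to 20 completers. But it is the ordinary consequence of a small pilot, and a sentence naming N would not reduce it. These figures rest on assumed n and normal data, and the Phase 2 ones also on the pilot SD applying unchanged to the trial outcome. The conclusion does not depend on which n is assumed. It would be different if the plan promised a power its size could not deliver, or if enrolment were to stop on the accumulating adherence results. The documents show neither.
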